The pharmacovigilance plan includes setting up a patient registry of type 2 diabetic patients taking lixisenatide. This would represent a proactive risk assessment in the post approval setting that allows for prospective follow-up and monitoring of occurrences of any of the outcomes of interest, i.e. pancreatitis, pancreatic cancer and thyroid cancer (especially medullary carcinoma of the thyroid).

The registry population will be representative of the population actually using the product since it should include all patients regardless of age, comorbidities or concurrent treatments. Follow up duration will be long enough to encompass delayed risks, consequences of long term use and effects of various combinations and alternations of treatments if any.

III.8 Research Question and Objectives

Study objectives

In the context of pharmacovigilance activity of the EU RMP (European Union Risk Management Plan), it has been agreed with the European Medicines Agency (EMA) to develop a Patient Registry of patients with diabetes exposed to lixisenatide.

The primary objectives of this study are to monitor the occurrences of:

- 1. acute pancreatitis,
- 2. pancreatic cancer
- 3. thyroid cancer, especially medullary carcinoma of the thyroid,

among adult type 2 diabetes patients treated with lixisenatide and to compare their risks with that of users of (1) other GLP-1 receptor agonists from the Database Study ; (2) other diabetic medications from the Database Study; and (3) the general population. The assembled cohort will be constantly monitored for these events to detect and emerging signal as quickly as possible.

Declaration of Study Hypotheses

This study is designed to focus on the risk associated with use of lixisenatide and will investigate the following primary hypotheses:

- 1. That adult patients prescribed lixisenatide have an increased risk of acute pancreatitis when compared to the expected risk calculated for the other GLP-1 RA users;
- That adult patients prescribed lixisenatide have an increased risk of pancreatic cancer when compared to the expected risk calculated for the other GLP-1 RA users;
- 3. That adult patients prescribed lixisenatide have an increased risk of thyroid cancer (especially medullary carcinoma of the thyroid) when compared to the expected risk calculated for the other GLP-1 RA users;

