- 3. A national hospital discharge registry, which covers the entire population included in the prescription database
- 4. A national death register, which can be used for record linkage to ascertain the date of death of any patient in the patient registry who died.
- 5. A source of information on key confounders (notably BMI), either in the prescription database itself, in a diabetes registry or in other available databases or large prospective studies.

A unique personal identity number will be used to link together the information from the several population based registries, as shown in the figure below:

The source of the cohorts will be mainly represented by the drug prescription registries.

The study population will include patients with type 2 diabetes treated with lixisenatide after launch. The study period will start from the lixisenatide launch and last for 5 years.

The patients will be identified as having been prescribed at least one prescription for the GLP-1 RA lixisenatide.

High completeness of follow-up is expected, as well as high accuracy of data, which will allow capture of the variables of most interest.

The study entry date will be defined as the date of the first prescription of lixisenatide after launch. The follow-up will end at the earliest of the following: 1) death or 2) the end of the register.

Data from national registers and databases in Denmark, Norway and Sweden will be used as the primary data source to identify lixisenatide treated patients for this registry. In Denmark, Norway and Sweden, national prescription databases have been established and are linkable to other national registers and databases (e.g., National Cancer Registry, Cause of Death Registry, and Hospital Discharge Registry) via National Registration Identification number.

A detailed table of characteristics of the cohort included in the analysis will be provided after consultation with the local investigators.

III.9.3 Variables (Outcome, Exposure, Risk factors, Confounding variables)

For each patient, information regarding all anti-diabetic medications prescribed in the study period will be recorded together with basic information such as age and gender.

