Patients who develop pancreatic cancer and thyroid cancer will be identified as well anyone who is diagnosed with pancreatitis, and their complete clinical information will be retrieved and collected from existing national registers and databases annually: smoking history, a previous diagnosis of Multiple Endocrine Neoplasia (especially MEN1), chronic pancreatitis, duration of diabetes, gallstones, prior use of other anti-diabetics, alcohol intake, obstruction of the pancreatic duct, radiation treatment to the head and neck, iodine intake, hormonal and reproductive treatment, diagnosis of Multiple Endocrine Neoplasia type 2 (MEN2), history of goitre or benign thyroid nodules, history of cancer, and family history of medullary thyroid cancer.

Outcomes of interest

Acute pancreatitis cases will be identified from the hospital discharge registers. Cases of thyroid cancer and pancreatic cancer will be identified from the national cancer registers. However, data on the cancer cases for a given year are typically considered incomplete until approximately one year after the year ends. For example, it will be possible to use the national cancer registries to identify incident cancers occurring until the end of 2013, if the analysis of thyroid cancer is planned to be performed in early 2015.

Exposure assessment and follow-up time

Patients with one or more prescriptions of lixisenatide will be identified from the national prescription registers and included in the register.

For acute pancreatitis, the exposure duration on lixisenatide will begin accumulating on the first day of lixisenatide prescription and continue with the subsequent continuous use of lixisenatide until:

- 1) the end of the lixisenatide treatment (in addition to a grace period of up to 30 days, to account for non-adherence),
- 2) the occurrence of acute pancreatitis, or;
- 3) the end of registry, whichever comes first.

For thyroid cancer and pancreatic cancer, the exposure duration will start from the first day of lixisenatide prescription and continue until either (1) the occurrence of thyroid cancer or pancreatic cancer, or (2) the end of registry, whichever comes first.

III.9.4 Data Sources

Patient registry data sources are the same as for the data base study (Section II.9.4)

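### The Registry's cancer rule keeps time as lixisenatide exposure after a switch to another GLP-1 RA and does not separate earlier GLP-1 RA users, so the comparison with other GLP-1 RA users (hypotheses 2-3) is contaminated

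*Protocol*

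**What the plan says.** Entry to the Registry needs a single prescription. Section III.9.2 has "The patients will be identified as having been prescribed at least one prescription for the GLP-1 RA lixisenatide", and section III.9.3 repeats it: "Patients with one or more prescriptions of lixisenatide will be identified from the national prescription registers and included in the register". Neither excludes, or sets apart, patients who used exenatide or liraglutide before.

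Section III.9.3 then fixes two exposure rules. For acute pancreatitis, time stops at "the end of the lixisenatide treatment (in addition to a grace period of up to 30 days, to account for non-adherence". For the two cancers there is no such stop: exposure starts on the first day of lixisenatide prescription and will "continue until either (1) the occurrence of thyroid cancer or pancreatic cancer, or (2) the end of registry, whichever comes first". Section III.9.2 adds death: "The follow-up will end at the earliest of the following: 1) death or 2) the end of the register".

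The first three primary hypotheses in section III.8 set lixisenatide against other users of the class; the second concerns an "increased risk of pancreatic cancer when compared to the expected risk calculated for the other GLP-1 RA users", and the first and third are built the same way.

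On drug data, section III.9.3 says that "information regarding all anti-diabetic medications prescribed in the study period will be recorded together with basic information". The study period begins at launch: "The study period will start from the lixisenatide launch and last for 5 years". Earlier anti-diabetic use appears only among the clinical details to be retrieved for patients who develop an outcome. Section III.9.7 plans a descriptive analysis and a yearly comparison of observed with expected counts.

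**The concern.** The comparison needs lixisenatide time on one side and other GLP-1 RA time on the other. The cancer rule mixes them within the Registry. A patient with one month of lixisenatide followed by four years of liraglutide contributes the whole period, and any cancer in it, to lixisenatide. So does a patient with years of liraglutide before a single lixisenatide prescription. Section II.9.1 expects many patients in these same countries to change treatment during the Database Study, so such histories should not be assumed rare.

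At stake is the reading of the Registry's cancer result. A ratio near 1 could mean that lixisenatide carries no more risk than its class, or that much of the time counted was not lixisenatide time. An excess could be due to lixisenatide or to what patients had taken before it. As planned, the Registry could not tell these apart.

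**Working it through.** **1. Does another section repair the rule?**
- Section II.9.7 gives the Database Study two analyses, one like intent-to-treat and one censored at end of treatment. Section II.9.3 adds a preference for new users and stratification by treatment history. Part III states none of these for the Registry.
- Section III.7 says follow-up should be long enough to cover combinations and alternations of treatment, but section III.9.7 gives no rule that uses them.
- Earlier drug use is collected for cases only, so it yields a numerator without person-years.
- The all-patient drug record covers the study period, which starts at launch. Section II.9.3 dates EU approval of exenatide to 28 November 2006 and of liraglutide to 2 July 2009, so prior use lies largely outside that record.

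**2. The plan's own figures** (section III.9.5, pancreatic cancer, 1% exposure)
- Person-years = 5 × 0.01 × 1,049,810 + 10 × 0.01 × 55,000 = 52,490.5 + 5,500 = 57,990.5, as printed.
- Expected cases E = 57,990.5 × 29.19 / 100,000 = 16.93, printed as 16.9.
- The formula counts every entrant in every later year, in line with the open-ended cancer rule.
- Exact Poisson power, one-sided 0.05 (critical count 25): 0.557 at a ratio of 1.5 and 0.952 at 2. Table III.9.5.2 prints 0.59 and 0.92. The agreement is rough; the printed values match E = 20 (0.597) and E = 15 (0.919), which suggests a look-up at rounded counts. The comparisons below use the exact values.

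**3. Effect of the affected time**

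Let f be the share of Registry cancer person-time that carries the comparator's rate, and R the true ratio for lixisenatide. Then

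apparent ratio = f × 1 + (1 − f) × R.

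For R = 2: f = 0.3 gives 0.3 + 1.4 = 1.7, and f = 0.5 gives 0.5 + 1.0 = 1.5. If that time is removed, the ratio stays at R and the expected count falls to (1 − f) × E: 11.85 at 30% and 8.46 at 50%. The values of f are assumptions.

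| True R | f | Apparent ratio | Power, plan's rule | Power, time removed |
|---|---|---|---|---|
| 2 | 0 | 2.0 | 0.95 | 0.95 |
| 2 | 10% | 1.9 | 0.92 | 0.93 |
| 2 | 20% | 1.8 | 0.86 | 0.90 |
| 2 | 30% | 1.7 | 0.78 | 0.86 |
| 2 | 50% | 1.5 | 0.56 | 0.79 |
| 1.5 | 0 | 1.5 | 0.56 | 0.56 |
| 1.5 | 30% | 1.35 | 0.35 | 0.42 |
| 1.5 | 50% | 1.25 | 0.23 | 0.39 |

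Thyroid cancer behaves alike at 5% exposure (17.8 expected): for R = 2, power falls from 0.96 to 0.80 at 30% and 0.58 at 50%, against 0.90 and 0.78 with that time removed.

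**4. When the direction is not fixed**

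Suppose there is no difference between the drugs, but prior users make up a share g of the time and have k times the expected rate. The ratio is then (1 − g) + g × k. If risk builds up over the class, k exceeds 1 and the ratio rises above 1. If susceptible patients have already left, k is below 1 and the ratio falls below 1.

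**The case against.** The strongest defence is that the cancer rule is deliberate. The Protocol gives the acute outcome an on-treatment rule and the cancers an ever-exposed one, and section II.9.3 draws the same line when it waives its three-month window for pancreatitis. With latency, a tumour found on liraglutide may stem from earlier lixisenatide, and cutting time at a switch could lose it. The intent-to-treat analysis of the Database Study offers a matching comparator. Censoring at a switch may be informative if symptoms prompt it. All this stands, and it is why the ever-exposed analysis should stay.

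It can also be said that strata belong in an analysis plan and that section III.9.1 foresees refinement before the Registry starts. That stands only in part: the exposure rule is fixed here, and it sets what counts as lixisenatide for a primary comparison.

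A reader might infer more than the documents support:
- *That the bias always runs towards no difference.* It does so only if risk follows the drug in current use.
- *That earlier users, having tolerated the class, lower the pancreatitis count.* The documents say nothing of the kind, and patients may equally have switched because they tolerated the first drug badly. The point is not made here.
- *That the comparator must be trimmed in the same way now.* Database cancer follow-up ends on 31 December 2012, and the positive CHMP opinion on lixisenatide dates from 15 November 2012, so there is essentially no lixisenatide time to remove.

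**Conclusion.** The concern holds for hypotheses 2-3. Followed exactly, the plan attributes time and cases on other GLP-1 RAs to lixisenatide and compares the result with other GLP-1 RA users. For hypothesis 1, pancreatitis time ends with treatment plus the grace period, so only the lack of separation of earlier users applies.

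The size cannot be fixed, because the documents give no share of switching or prior use. On the assumption that affected time carries the comparator's rate, each 10% of it removes 10% of the excess. At a 10% share the power loss for a true doubling is small (0.95 to 0.92); at 30% to 50% it is material, and removing that time does better despite fewer cases. If risk does not follow current use, neither the direction nor these figures apply, but the result remains hard to attribute to lixisenatide.

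**What to change.** Keep the ever-lixisenatide cancer analysis, and add to sections III.9.3 and III.9.7:

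1. A prespecified cancer analysis for hypotheses 2-3 that censors, with a stated lag, at the first prescription of another GLP-1 RA. Section II.9.3 already works with three months and a six-month sensitivity analysis, which could serve as a starting point.
2. Results for hypotheses 1-3 split by GLP-1 RA-naive and prior GLP-1 RA users at entry, with status taken from A10 prescriptions before launch as well as during the study period, for all entrants and not only for cases.

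End other GLP-1 RA comparator time at the first lixisenatide prescription only if the database follow-up is extended past the lixisenatide launch.

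The cost is wording and programming, since section III.9.4 already retrieves A10 users from the prescription registers. The price in information is fewer expected cases in the uncontaminated set (11.85 instead of 16.93 at a 30% share) and possible informative censoring at a switch. The ever-exposed analysis stays alongside for that reason.

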Final study report	2017 for Acute pancreatitis		
	2019 for pancreatic and thyroid cancer		

III.7 Rationale and Background

GLP-1 RAs have been a focus of attention since the signalling of certain (rare but serious) adverse effects reported with their use: pancreatitis, pancreatic cancer and thyroid cancer (especially medullary carcinoma, a rare tumour of the thyroid gland).

Glucagon-like peptide 1 receptor agonist (GLP-1 RA) is a new class of blood glucose lowering drugs indicated in the treatment of type 2 diabetes mellitus (T2DM). It is an agonist molecule to the incretin (gastrointestinal hormone) GLP-1 which stimulates glucose-dependant secretion of insulin. GLP-1 is rapidly inactivated by the dipeptdyl peptidase-1 (DPP-4) (half life of about 2 minutes), hence the need for a GLP analogue or agonist with greater resistance to DDP-4 degradation. GLP-1 regulates glucose levels by stimulating glucose-dependent insulin secretion and biosynthesis, and by suppressing glucagon secretion, delayed gastric emptying and promoting satiety.

There are currently 2 GLP-1 RA products on the market, one of which (exenatide) is available in two formulations (Byetta and Bydureon):

- Exenatide (also Exendin-4) marketed as Byetta by Amylin Pharmaceuticals, Inc., (San Diego, California, United States of America was launched in 2005 in the USA and approved in 2006 in the European Union and is administered subcutaneously twice daily; Exenatide marketed as Bydureon by Amylin Pharmaceuticals, Inc., (San Diego, California, United States of America) was approved on the market in 2012 and is administered subcutaneously once weekly.

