Using these hypothetical numbers, the number of patient-years accumulated over a period of 5 years of registry were calculated as follows:

1st year of registry: no records yr1 = %lixi * prevalence diabetes = %lixi * 1,049,810 2nd year of registry: no records yr2 = no records yr1 + new records yr2= no_records_yr1 + %lixi * new_cases_diabetes = no_records_yr1 + %lixi * 55,000 3rd year of registry: no_records_yr3 = no_records_yr2 + new_records_yr3 = no_records_yr1 + 2 * %lixi * new_cases_diabetes

etc...

Thus the number of person-years accumulated over 5 years is: Person-years_over_5_years = no_records_yr1 + no_records_yr2+..+ no_records_yr5 =5*(%lixi*prevalence_diabetes)+10*(%lixi*new_cases_diabetes)

The number of expected cases of pancreatitis were calculated using the incidence rate shown above (65.57 per 100,000 person-years). The power of the study was then calculated for the expected number of cases as a mean of Poisson law (Breslow and Day, 1987) and a range of expected vs observed ratios. The results are shown in Table III.9.5.1.

Table III.9.5.1: Estimates of statistical power for Registry Study for pancreatitis under different scenarios for prevalence of prescription of lixisenatide.

Pancreatitis (incidence rate=65.57/100,000 pyrs)						
	Pyrs No of Power in order Power in order Power in o					
% exposure to	accumulated	expected	to detect	to detect	to detect	
lixisenatide	over 5 years	cases	obs/exp+=1.2	obs/exp+=1.5	obs/exp+=2	
0.10%	5799.05	3.8	0.10*	0.17	0.39	
0.20%	11598.1	7.6	0.13*	0.26	0.64	
0.50%	28995.25	19.0	0.18	0.60	0.97	
0.80%	46392.4	30.4	0.27	0.79	1.00	
1.00%	57990.5	38.0	0.29	0.83	1.00	
1.50%	86985.75	57.0	0.37	0.93	1.00	
2%	115981	76.0	0.47	0.98	1.00	
5%	289952.5	190.1	0.38*	1.00	1.00	
10%	579905	380.2	0.60*	1.00	1.00	
*Calculated using normal approximation						
tobs /exp stands for 'observed us expected ratio'						

+obs/exp stands for 'observed vs expected ratio

These numbers are certainly underestimated, as the incidence of diabetes has been steadily increasing worldwide. Even so, for a 1% exposure to lixisenatide among diabetic patients, thus 38 expected cases of pancreatitis, the power of the study in order to

detect an observed vs expected ratio of pancreatitis of 1.5 will be of 83% (significance level=0.05).

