² An external blinded committee (Pancreatic Safety Assessment Committee or PSAC) has been appointed to review all pancreatic adverse events occurring in clinical trials of lixisenatide. The PSAC Charter has not been finalized, yet. However, the criteria for adjudication of acute pancreatitis will be adapted from those proposed by Banks, Freeman, and the Practice Parameters Committee of the American College of Gastroenterology (Am J. of Gastroenterology 2006;101:2379-2400) and Frossard et al. (Lancet 2008;371:143-52.).

Similarly to the Database Study, each national centre will be responsible for the data storage and data management of the individual-level data, following all national and European directives regarding the well being and rights of each study subject. Each centre has an excellent track record of successfully undertaking similar research respecting all moral and legal requirements.

Only de-identified data will be stored at IPRI, and this will be done in a secure manner: data will password protected, and stored on local machines.

III.9.7 Data Analysis

Descriptive analysis will be performed and total follow-up time for lixisenatide users will be calculated.

Figure II.9.7.3: General study overview

For acute pancreatitis, pancreatic cancer and thyroid cancer, the expected number of cases will be estimated annually after launch using the background rates obtained from the retrospective databases study.

If the observed number of cases for the events of interest, respectively, is significantly higher than the expected number of cases, further investigation may be warranted following discussion with the regulatory authorities.

An independent **Scientific Steering Committee** will be appointed to oversee the study and advise on treatment, methodological and biostatistical issues. This group will meet regularly throughout the duration of the study and incorporate a **Biostatistical Advisory Group**, to advise on all aspects of the design and data analysis.

The Scientific Steering Committee will comprise:

[name] University of Perugia Perugia, Italy

[name] University College London London, United Kingdom

[name] Robertson centre for Biostatistics University of Glasgow, Glasgow, United Kingdom

[name] Department of Biostatistics Yale University School of Public Health New Haven, United States of America

[name] McMaster University, Hamilton, Canada

[name] Mount Sinai Hospital New York, United States of America.

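### The Registry's 83% power for acute pancreatitis rests on five full years per user with nobody stopping, while the design counts on-treatment time only and reports in 2017

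*Protocol*

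**What the plan says.** Section III.9.5 (Study Size) takes 1,049,810 prevalent patients with diabetes and about 55,000 new cases a year. It places the chosen percentage of all prevalent patients in year 1 as whole person-years, adds the same percentage of new cases in each later year, and carries every record forward. The five-year total is "5*(%lixi*prevalence_diabetes)+10*(%lixi*new_cases_diabetes"). There is no term for gradual uptake, stopping or death.

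The power statement built on it reads "for a 1% exposure to lixisenatide among diabetic patients, thus 38 expected cases of pancreatitis", with power to "detect an observed vs expected ratio of pancreatitis of 1.5 will be of 83% (significance level=0.05"). The synopsis of the Registry protocol repeats the figure. III.9.5 then adds: "These numbers are certainly underestimated, as the incidence of diabetes has been steadily increasing worldwide".

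Three other places bear on the same person-time:

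- III.9.3 ends pancreatitis exposure at the first of several events, one of which is "the end of the lixisenatide treatment (in addition to a grace period of up to 30 days, to account for non-adherence").
- III.9.2 ends follow-up at death or at the end of the register, and sets a study period of five years from launch.
- III.6 ends data collection in 2018 but gives the final study report as "2017 for Acute pancreatitis".

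**The concern.** The expected number of cases drives the power, and it is proportional to person-years. If the person-years in the power table include time the analysis will not count, the power is overstated. For pancreatitis this happens in two ways: time after a user stops lixisenatide is in the formula but excluded by III.9.3, and the last part of the five years is in the formula but may not be available for a 2017 report. Deaths are a further, smaller omission.

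This is a safety registry whose signal rule is that if the observed count "is significantly higher than the expected number of cases, further investigation may be warranted". If power is overstated, a finding of no excess looks more reassuring than it is. The sentence calling the numbers underestimates points readers the wrong way: it mentions only rising diabetes incidence, and none of the assumptions that work in the opposite direction.

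**Working it through.** **Inputs from the Protocol (III.9.5).** At 1% exposure, N = 0.01 × 1,049,810 = 10,498.1 users at the start and M = 0.01 × 55,000 = 550 new users a year. The background rate is 65.57 per 100,000 person-years, the ratio is 1.5 and the significance level is 0.05. Sidedness is not stated; the signal rule is upper-tail, and a one-sided test reproduces the table.

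**Person-years as planned.** 5N + 10M = 52,490.5 + 5,500 = 57,990.5. Times 65.57/100,000 this is 38.02 expected cases. Both match Table III.9.5.1.

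**Power method.** With E expected cases, take the smallest c with P(X ≥ c | E) ≤ 0.05; power is P(X ≥ c | 1.5E), X Poisson.

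- E = 38.02: c = 49, power 0.872.
- E = 35: c = 46, power 0.833, which is the stated 83%.

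Other rows also match rounded values of E: 30 gives 0.79, 20 gives 0.60, 50 gives 0.93 and 70 gives 0.98. The 83% therefore looks like a look-up at E = 35. That leaves a cushion: 35 / 38.02 = 0.92, so about 92% of the assumed person-time must be on treatment by the cut-off to keep 83%.

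**Cut-off only (full uptake, no stopping).** Four full years: 4N + 6M = 41,992.4 + 3,300 = 45,292.4 person-years, E = 29.7, c = 40, power 0.77. At 4.5 years E = 33.9 and power is 0.81; at 4.9 years E = 37.2 and power is 0.87.

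**Stopping only (five years; the rates are assumptions).** Let d be the yearly stopping fraction, s = 1 − d and h = −ln s. If loss begins at once, a user followed for T years contributes (1 − s^T)/h. If the first year is kept whole, the contribution is (1 − s^T)/d. Sum over N users with T = 5 and M users each with T = 4, 3, 2, 1.

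| Assumed yearly stopping | Loss from day one: person-years, E, power | First year whole: person-years, E, power |
|---|---|---|
| 10% | 45,527; 29.9; 0.78 | 47,968; 31.5; 0.79 |
| 20% | 35,669; 23.4; 0.66 | 39,796; 26.1; 0.71 |
| 30% | 27,920; 18.3; 0.56 | 33,195; 21.8; 0.64 |

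**Both together (four years, loss from day one).** 10%, 20% and 30% stopping give E = 24.4, 19.9 and 16.1, and power 0.69, 0.59 and 0.55.

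**Does rising diabetes incidence offset this?** New cases supply 5,500 / 57,990.5 = 9.5% of the person-years. Doubling them over four years with nobody stopping gives 4N + 12M = 48,592.4 person-years, E = 31.9 and power 0.82, still short of 83%.

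Exact Poisson power moves in small jumps as E changes, so differences of one or two points between scenarios mean little.

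**The case against.** **The percentage is a scenario, not a forecast.** III.9.5 calls its numbers hypothetical, and the table runs from 0.1% to 10%. If 1% meant a constant share of current users, those who stop would be replaced. This has some force: a slow uptake curve partly redefines the 1% scenario, so no uptake figure is used above. But the formula accumulates records and never replaces anyone, the scenarios vary only the percentage and not the time per user, and the 2017 date remains on either reading.

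**The 2017 report may cost little.** This stands in part. Data collection ending in 2018 after five years implies a 2013 start, so a 2017 report would hold roughly four to just under five years. With no stopping, the cut-off alone costs between almost nothing and about six points against the stated 83%. III.6 also allows an earlier final analysis once enough participants are captured, but it does not say how many are enough.

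**The size is not in the document.** Correct. No persistence or uptake rate is given, and the stopping rates above are assumptions.

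**Power will be refined, and follow-up will be reported.** III.9.5 says power will be further defined, and expected cases are recalculated annually. That limits the harm, but it does not reconcile a headline figure with the exposure rule in the same protocol.

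**A reader might infer that the cancer figures fail in the same way.** The document does not support that. III.9.3 does not end cancer exposure when treatment stops, so leaving out stopping is consistent there. On the register lag illustrated in III.9.3, a 2019 report could cover most of year five. Even four full years give 45,292.4 × 29.19/100,000 = 13.2 expected pancreatic cancers and power 0.92 for a ratio of 2, equal to the stated figure.

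**Conclusion.** The point holds for acute pancreatitis. The arithmetic in III.9.5 is correct: 57,990.5 person-years and 38.0 expected cases reproduce exactly. The fault is that these person-years are not the ones III.9.3, III.9.2 and III.6 define for this outcome. The direction of the error is clear from the text, because stopping, death and an early cut-off can only reduce the count. Its size is not. The stated 83% is kept only if about 92% of the assumed person-time is on treatment by the cut-off. Under full uptake, power is about 77% at four years without stopping, and about 78–79% down to 56–64% over five years with assumed stopping of 10% to 30% a year.

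A reader might go further and say that 83% has been shown to be unattainable. That does not follow: with high persistence and a cut-off late in 2017 it could still be reached. What can be said is that the Protocol gives no basis for expecting it.

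**What to change.** 1. Recompute the pancreatitis power in Table III.9.5.1, and the matching synopsis sentence, on on-treatment person-years (including the grace period) available at the actual data cut-off. State the persistence and uptake scenarios used, allow for deaths, and state whether the test is one-sided.
2. Reconcile the 2017 pancreatitis report date in III.6 with the 2018 end of data collection. Either state the cut-off and base the power on it, or place the report after the fifth year.
3. Delete the sentence in III.9.5 calling the numbers underestimates, or qualify it by naming the assumptions that work the other way.
4. Leave the cancer power in Table III.9.5.2 as it stands on this point; an uptake sensitivity analysis there is optional.

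The cost is a recalculated table and a few changed sentences. The stated power for pancreatitis will probably fall. No patients, data sources or procedures are added, since the Registry already takes all users.
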